Prior data including the FLAME trial (8) show improvement in biochemical control, but meta analyses have criticised this endpoint. The Meta-Analysis of Randomised Trials in Cancer of the Prostate (MARCAP) investigators conclude that “Overall, these results strongly suggest that biochemical recurrence based endpoints should not be the primary end point of any randomised trial in localised PCa” (63). The proposed trial here is thus needed to investigate the clinical relevance of intraprostatic boosting with modern RT techniques using a more strict endpoint.

Nevertheless, biochemical control remains a commonly used endpoint and correlates heavily with the clinically relevant endpoint of onset of salvage hormonal therapy (63). It has also been repeatedly shown to correlate with radiation dose (64) and can thus be valuable for testing heterogeneity of treatment effect between techniques used in the involved clinical sites. We therefore perform a full power assessment of this important secondary endpoint.

The effect size for focal boost under the alternative hypothesis is assumed to be $HR=0.45$ for biochemical control (the estimate from 8) leading to greater than 90% power on a two-sided test for superiority with 1,016 patients.

The factorial design performs best when there is no interaction between the interventions. A test for interaction can be made by a within-the-table comparison as supplement to the main analysis at the margins (65, 66). These tests will be performed with biochemical control as the endpoint to optimise power.

In addition, tests for heterogeneity of treatment effects across the technological approaches to subvolume boosting (e.g. MR-linac based versus CT based versus proton therapy) will be performed on the endpoint of biochemical control for optimal power.

Further secondary endpoints

- Time to next treatment for prostate cancer.

- Regional relapse-free survival (rRFS)
- Overall survival (OS)
- Self-reported quality of life (QoL)

Pre-planned analyses during accrual

A number of pre-planned analyses will be conducted during the trial accrual period. Influence on the primary outcome p-values is avoided by 1) refraining from analysing efficacy endpoints before trial completion and 2) blinding the analysis of radiation dose response to trial arm in the planned dose response study. Therefore, no adjustment for multiplicity of tests is made on the primary endpoints.

Acute toxicity after 400 patients

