Subjects will accordingly to standard practice be followed for 10 years with a blood sample (PSA) monitoring disease control, whereas toxicity and quality of life (QoL) will be followed for 5 years. Testosterone is measured accordingly to local practice. Survival will be followed for up to 20 years. Additional visits beyond those established by the protocol will follow local guidelines. Protocol visits can be conducted by phone or video meeting, if preferred.

Data will be collected at follow-up visits as shown in the figure below

	Department of Urology 1. ADT	Department of Oncology Baseline Inclusion	Radiotherapy 20 fx 12 fx	3 months after start of RT 2. ADT	1 year 4. ADT	2 years 6. ADT	3 years	4 years	5 years	6-10 years
Months	-3	-1	0	3	15	27	39	51	63	75, 87, 99, 111, 123
Physical exam		x								
PSA	x	x		x	x	x	x	x	x	x
Testosterone*		(x)		(x)	(x)	(x)	(x)			
Biomarkers		x		x						
CTCAE		x		x	x	x			x	
PRO's and QoL		x		x	x	x			x	

* Recommended, but can be according to local practice

Toxicity registration

Gastrointestinal (GI) and genitourinary (GU) toxicities will be assessed according to Common Terminology Criteria for Adverse Events (CTCAE) v5.0. Acute toxicity is defined as adverse effects occurring within 90 days of the first radiation treatment, while late toxicity is defined as effects occurring 90 days or more after the first treatment. Toxicities will be analyzed in relation to dose-volume histograms (DVHs) for organs at risk (OARs), including the bladder, urethra, and rectum, as well as target structures, such as the gross tumor volume (GTV), clinical target volume (CTV), and planning target volume (PTV).

Patient-reported outcome measures (PROM) will include EORTC QLQ-PR25 and QLQ-C30.

PROM questionnaires will be sent to the patient's digital mailbox at predefined dates and to ensure a high response rate, the system will be configured to send automated reminders in case of missing responses. Data will be filed and stored using eCRFs in a REDCap database.

The data management system ensures compliance with current legislation and regulations on data handling and data safety. Sponsor, sponsor's representatives, investigators and controlling authorities have direct access to the above mentioned data including access to electronic patient records in order to ensure data quality and to monitor data quality.

Adverse Events (AEs) and Serious Adverse Events (SAEs)

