During follow-up after radiotherapy (up to 60 months), all radiation-induced SAE will be reported and followed.

Due to the severity of the disease in this study, the following situations are excluded from expedited notification on a SAE form and should instead be reported in the Case Report Form (CRF) follow-up form.

- Elective hospitalisation to simplify treatment or procedures
- Elective hospitalisation for pre-existing conditions that, in the investigator's opinion, have not been exacerbated by trial treatment

- Disease progression
- Death as a result of disease progression

All SAE must be reported to sponsor within 1 working day.

Sponsor reports all SUSARs (Suspected Unexpected Serious Adverse Reactions) to the Ethics Committee within 7 days, if life threatening or fatal, and within 15 days, if not life threatening. Sponsor will annually report all SAEs to the Ethics Committee.

Endpoints

Primary endpoint

- Freedom from distant metastasis (FFDM)

Secondary endpoints

- Freedom from biochemical relapse
- Time to salvage hormonal therapy
- Regional relapse-free survival (rRFS)
- Local relapse-free survival (rRFS)
- Overall survival (OS)
- Prostate cancer specific survival
- Self-reported quality of life (QoL)
- Toxicity as CTCAE

Disease related endpoints are calculated from randomisation to event.

Recommended work-up at suspected recurrence

Diagnostic workup on suspicion of recurrence takes place according to national guidelines as described below.

PSMA PET/CT is recommended:

- If a recurrence is suspected biochemically according to the Phoenix criteria
- If a recurrence is suspected clinically, e.g: Bone pain, anemia, urinary symptoms
- If recurrence is suspected by radiographic test

If PSMA PET/CT shows no sign of regional or distant metastases, a diagnostic mpMRI of the prostate is recommended. Local recurrence after definitive radiotherapy should be confirmed by biopsy from the site of suspected recurrence if the result has implication for the treatment.

Cancer related endpoints

Events are: occurrence of distant metastases, castration resistance, biochemical relapse as defined by Phoenix criteria (PSA nadir + 2) (76), start of endocrine treatment, local recurrence, regional recurrence, and death.

Distant metastasis

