The event distant metastasis can be detected radiographically as PSMA PET/CT is recommended at suspicion of relapse. Biopsy is also accepted and MRI, CT, bone scintigraphy, NAF-PET, ultrasound or clinical examination may also be accepted with further confirmation, e.g. biopsy or laboratory tests. If the event “distant metastasis” is based on tests without biopsy or PSMA positivity the event shall be confirmed at MDT.

Biochemical relapse

Phoenix criteria are used for definition of the event biochemical relapse, defined as a PSA increase of 2 ug/l from nadir. The date of recurrence is the first date with a PSA level of nadir + 2. The PSA level must be confirmed by a second PSA measurement performed at minimum two weeks later.

Local recurrence

The event local recurrence is defined as a local PSMA positive lesion. Local recurrence after definitive radiotherapy should be confirmed by biopsy from the site of suspected recurrence if the result has implication for the treatment. MRI, CT, ultrasound or clinical examination may also be accepted with further confirmation, e.g. biopsy.

Regional relapse

The event regional recurrence is defined as at least one regional PSMA positive lesion. Biopsy is also accepted and MRI, CT, ultrasound or clinical examination may also be accepted with further confirmation, e.g. biopsy or laboratory tests. If the event “distant metastasis” is based on tests without biopsy or PSMA positivity the event shall be confirmed at MDT.

Death

Cause and time of death is collected from electronic patient charts for up to 20 years. If no information is available, data will be retrieved from the national death register.

Endpoints related to toxicity

Self-reported quality of life (QoL)

QoL is registered as described in the paragraph “Follow-up and Data Collection” using EORTC QLQ-PR25 and QLQ-C30.

CTCA registered toxicity

Toxicity is registered using CTCAE v 5.0 as described in the paragraph “Follow-up and Data Collection”

Radiotherapy Quality Assurance (QA)

[figure not shown]
The radiotherapy (RT) approach in this study is a highly advanced treatment combining several modalities. Tumour targets are identified by multi-parametric MRI, PET and CT. The individualised dose-plans are optimised for tumour dose while minimising doses to healthy critical tissue. The treatment is delivered by linear accelerators using daily on-line imaging and treatment adaptation.

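### Biochemical relapse needs a confirming second PSA with no exception for salvage treatment started first, so a treated relapse can stay counted as free from biochemical relapse

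*Protocol*

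**What the plan says.** The Biochemical relapse section of the protocol sets three things.

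- Threshold: "Phoenix criteria are used for definition of the event biochemical relapse, defined as a PSA increase of 2 ug/l from nadir".
- Date: "The date of recurrence is the first date with a PSA level of nadir + 2".
- Confirmation: "The PSA level must be confirmed by a second PSA measurement performed at minimum two weeks later".

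It gives no maximum interval to the second sample, no other route to the event, and no rule for treatment started in between.

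The introductory list under Cancer related endpoints names the same event as Phoenix nadir + 2 and does not mention confirmation. That list also contains "start of endocrine treatment, local recurrence, regional recurrence, and death", each as an event type beside biochemical relapse and not as part of it. Under Secondary endpoints, "Time to salvage hormonal therapy" is an endpoint of its own.

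Recommended work-up at suspected recurrence gives three triggers for PSMA PET/CT: Phoenix suspicion, radiographic suspicion, and clinical suspicion ("If a recurrence is suspected clinically, e.g: Bone pain, anemia, urinary symptoms"). None requires a confirmed PSA, and the last two carry no PSA threshold.

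On follow-up, the protocol says: "Subjects will accordingly to standard practice be followed for 10 years with a blood sample (PSA) monitoring disease control". The visit table has a PSA at 3 months and then yearly from month 15, with no confirmatory visit.

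Secondary endpoints with formal power assessment claims more than 90% power for biochemical control at HR 0.45. On the factorial interaction it says: "These tests will be performed with biochemical control as the endpoint to optimise power". The test of heterogeneity across boost technologies uses the same endpoint.

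**The concern.** Hormonal therapy lowers PSA. If it starts after a first PSA at nadir + 2 but before the second sample, the second sample may fall below the threshold and the mandatory confirmation fails. If it starts on a positive scan or on symptoms before nadir + 2, the threshold may never be reached. Either patient is on treatment for recurrence, yet read literally has no biochemical event.

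Three uses of the endpoint are exposed: the formal secondary power claim, the boost-by-fractionation interaction test and the technology heterogeneity test. Equal loss of events in the two arms costs power. Unequal loss also biases the HR. Unequal loss is possible because the protocol describes no blinding of the clinicians who decide on imaging and salvage treatment.

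**Working it through.** **Inputs from the protocol**

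- Reference 5-year biochemical control 87%, dropout hazard 0.039 per year (Statistical considerations).
- HR 0.45, two-sided test, 1,016 patients, so 508 v 508 at the boost margin (Secondary endpoints with formal power assessment).
- 5 years of uniform accrual plus 1 year (stated for freedom from distant metastasis, FFDM; assumed to apply here).

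**Assumed:** alpha 0.05, which is not stated for this test, and exponential hazards.

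**Step 1: hazards.** Without boost, l0 = -ln(0.87)/5 = 0.02785 per year. With boost, l1 = 0.45 × 0.02785 = 0.01253.

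**Step 2: expected events.** With h = l + 0.039 and follow-up uniform on 1 to 6 years,

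P(event) = (l/h) × [1 - (e^(-h) - e^(-6h))/(5h)].

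- No boost: h = 0.06685, P = 0.0854, × 508 = 43.4 events.
- Boost: h = 0.05153, P = 0.0396, × 508 = 20.1 events.
- Total 63.5. Without dropout: 46.8 + 21.7 = 68.5.

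**Step 3: the plan's own power.** Schoenfeld: power = Φ(√d/2 × |ln HR| - 1.96), with |ln 0.45| = 0.7985.

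- d = 68.5 (no dropout): 91.1%.
- d = 63.5 (dropout): Φ(3.181 - 1.960) = 88.9%.

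The Freedman form gives 88.1% and 85.6%. The stated figure of more than 90% therefore reproduces without dropout and comes within about a point of 90% with it. Power of 90% needs 4 × (1.960 + 1.282)²/0.7985² ≈ 66 events, so there is almost no reserve at 5+1 years.

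**Step 4: loss of events.** The protocol gives no rate of salvage treatment before confirmation, so the shares below are assumptions. Equal loss scales d by (1 - f). Unequal loss thins each arm's hazard, giving apparent HR = 0.45 × (1 - f_boost)/(1 - f_no boost). All rows include dropout.

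| Lost, no boost | Lost, boost | Events | Apparent HR | Power |
|---|---|---|---|---|
| 0% | 0% | 63.5 | 0.45 | 88.9% |
| 10% | 10% | 57.1 | 0.45 | 85.5% |
| 20% | 20% | 50.8 | 0.45 | 81.2% |
| 20% | 10% | 53.2 | 0.45 × 0.9/0.8 = 0.51 | about 70% |
| 10% | 20% | 55.4 | 0.45 × 0.8/0.9 = 0.40 | about 93% |

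In the last row the higher power comes from an overstated effect and is no gain. Apparent 5-year control in the reference arm rises from 87% to 88.2% with 10% lost and to 89.5% with 20% lost.

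**Step 5: longer follow-up.** At 5+5 years with dropout, 122 events are expected and power is 99.3%; an equal 20% loss leaves 97.7%. The loss of power is thus a matter of the early analysis. The shift in HR under unequal loss does not shrink with follow-up.

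**The case against.** **Silence is not exclusion.** The protocol never says that salvage treatment does not count, the consensus it cites for the Phoenix criteria is not at hand, and a statistical analysis plan is promised before data analysis. That is fair for salvage started before any PSA at nadir + 2, where the text is merely silent. It does not cover the second PSA: confirmation is mandatory and has no exception, so an analysis plan that counted an unconfirmed rise would depart from the protocol.

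**The patients are captured elsewhere.** They count for time to salvage hormonal therapy, for the local and regional endpoints and, if metastatic, for FFDM. This is true, and it is why the primary endpoint is untouched. It does not repair the endpoint that carries the power claim and the interaction and heterogeneity tests.

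**The mechanism may be rare.** Two weeks is short, extra visits follow local practice, and a second PSA can be drawn during work-up. This stands: the frequency is unknown.

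**Counting salvage start brings open-label judgement into a laboratory endpoint.** This also stands. It argues against making salvage start a full component of the main definition and for showing both analyses.

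A reader might infer that the worst relapses are the ones that disappear, or that the boost effect will be understated. The documents support neither. Nothing says that severe relapses are treated before confirmation, and the imbalance between arms could run either way.

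**Conclusion.** The point holds as a defect in how a secondary endpoint is fixed. The definition requires confirmation without exception, the event list omits confirmation, and the work-up does not wait for it. A patient on salvage treatment can therefore remain biochemically controlled.

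Its size is conditional. At 5+1 years, two-sided 0.05 and dropout 0.039, an assumed equal loss of 10-20% of about 63 events takes power from about 89% to about 86-81% with no bias in the HR. A 20% v 10% imbalance moves the apparent HR from 0.45 to about 0.51 or 0.40. The loss shares, the alpha and the 5+1-year horizon for this endpoint are assumptions. The trial's primary conclusion on FFDM is not at risk. The change is worth making because it is cheap and the endpoint supports several planned tests.

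**What to change.** 1. Reconcile the event list under Cancer related endpoints with the Biochemical relapse section, so that both state the same rule on confirmation.
2. State that a first PSA at nadir + 2 counts as the event, dated at that PSA, without confirmation when salvage treatment starts before the second PSA.
3. For salvage treatment started before any PSA at nadir + 2, count salvage start as an event in a pre-specified analysis reported beside the PSA-based one. Planned adjuvant ADT or abiraterone is not salvage.

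The cost is one definition paragraph and one derived variable. Start dates of hormonal salvage are already needed for a listed endpoint, and the time to next treatment listed among the further secondary endpoints needs the others. The downside is that salvage start is an open-label decision, so both analyses should be shown. The change concerns event counting only and says nothing about when patients are scanned or treated.

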- Dose constraints for organs at risk are kept according to guidelines in this protocol
- Guidelines for IGRT according to institutional protocol.
- Treatment is delivered with institutional protocols that fulfil the goals and constraints given in this protocol (appendix B).

Radiotherapy

Radiotherapy planning:

Modern RT planning is wholly dependent on high level computing. This allows for creation of highly personalised dose plans with several different dose levels within the same plan. Additionally, these plans exhibit sharp dose gradients towards critical organs at risk (OAR). Depending on treatment modality plans will either use a simultaneously integrated or sequential boost. In the former case the treatment session delivers a boost to the intraprostatic lesion (if randomised for boost) in addition to the prescribed doses to prostate and elective targets. In the latter case prescribed doses to prostate and elective targets are delivered in the same treatment sessions whereas a boost will be delivered in separate sessions using specialised equipment e.g. an MR-Linac. In either case the dose planning will seek to minimise the trade-off between sufficient target coverage - usually between 95% and 107% of the prescribed target doses - and reducing as much as possible the doses to OAR. It is not uncommon that requirements for target and OAR doses are mutually exclusive. The order in which every dose requirement should be prioritised is detailed in Appendix B as well as specific

requirements to target coverage. To ensure that the dose planning of all participating centres will be vetted as part of the comprehensive RT-QA program described in Appendix A.

Rectal and bladder preparation protocol:

Patients should be treated with a comfortably filled bladder and an empty rectum/bowel according to local protocol. Use of Image Guided Radiotherapy (IGRT) is mandatory to ensure the elective target coverage and to assess bladder- and rectal filling. Application of a bladder-filling protocol in an attempt to decrease the volume of bladder irradiated is recommended using IGRT to check the target positioning.

Target volume definition, dose and fractionation:

Delineation of the targets are performed on the treatment planning MRI, guided by both the diagnostic multiparametric MRI (mpMRI) and PSMA-PET CT scan. Organs at risk (OARs) are delineated on the planning CT scan.

Fractionation:

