- 20 fractions, no boost: Prostate and seminal vesicles: 60 Gy/ 20 fractions. Pelvic: 45 Gy /20 fractions.
- 20 fractions, boost: Boost 75 Gy/20 fractions, prostate and seminal vesicles: 60 Gy/ 20 fractions. Pelvic: 45 Gy /20 fractions.
 - If a boost is delivered on special equipment, such as an MR accelerator, it is allowed to give the boost in fewer fractions with same equivalent dose and maintaining same overall treatment time
- 12 fractions, no boost: Prostate and seminal vesicles: 50 Gy/ 12 fractions, Pelvic: 37 Gy /12 fractions.
- 12 fractions, boost: Boost 60 Gy/12 fractions, prostate and seminal vesicles: 50 Gy/12 fractions, Pelvic: 37 Gy /12 fractions.
 - If a boost is delivered on special equipment, such as an MR accelerator, it is allowed to give the boost in fewer fractions with same equivalent dose and maintaining same overall treatment time

All treatments with 5 fractions per week

Intraprostatic lesion(s): If a boost is to be performed, the most dominant lesion(s) are contoured as GTVp_FB_post with the prefix 1, 2 etc. according to the number of lesions with the use of information from the planning MRI and PSMA-PET/CT used as guidance. As the lesions and the prostate gland normally decrease in size with neoadjuvant ADT, a CTVp_FB_final should be created. This volume should not only include the GTVp_FB_post but also account for the potential initial tumor volume (GTVp_FB_pre) as observed on the diagnostic MRI performed prior to initiating ADT. The three sequences used from mpMRI are:

- 1) T2 weighted image, where the tumour lesions appear in grey
- 2) DWI (Diffusion Weighted Imaging), where the tumour lesions appear as white areas
- 3) ADC (Apparent Diffusion Coefficient), where the tumour lesions appear as black areas

CTVp_FB should be included in the CTVp or CTVp_SV. No margin is used for intraprostatic lesions.

For radiation target nomenclature, see appendix C

Prostate: MRI is used to contour the CTVp volume as the whole gland with any visible extracapsular extension of disease included.

Elective pelvic lymph nodes: If N1, elective lymph nodes should be delineated according to NRG Oncology Updated International Consensus Atlas on Pelvic Lymph Node Volumes for Intact and Postoperative Prostate Cancer, 2021 (74). Elective pelvic lymph node area is named CTVn_E. Any clinically suspicious lymph nodes should be included in the CTVn_E. PTV is derived by adding a 5-10mm margin to CTVp, CTVp_SV and CTVn_E. See appendix D

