The potential advantages for a patient participating in the trial is to have fewer fractions in the experimental arms (12 fractions versus the standard arm of 20 fractions), and to reduce the risk of distant metastases by increasing the dose to the intraprostatic tumor lesion.

Potential risks for the patient

The potential disadvantage for the patient is an increased risk of late side effects from the lower urinary tract and rectum and bowel.

The side effects and risks of curatively intended combined LHRH-treatment, and radiotherapy for prostate cancer is well described and the patients will be informed about the risks before treatment.

We cannot exclude an increased risk of urinary and/or genito-urinary toxicity in the short treatment arm as the primary endpoint is non-inferiority for increased toxicity. A careful collection of recorded toxicity is therefore an important part of the study. An independent data monitoring committee will oversee the data during the study (see paragraph on independent data monitoring committee).

The concept of the study is to test if increased dose to intra prostatic lesions without increased dose to the surrounding organs improves tumour control. For the patients in the boost arm, we will also ensure that dose to urethra is kept the same dose level as the non-boost arm. However, we cannot completely exclude a higher risk of urinary toxicity.

Withdrawal of consent

The participant can withdraw from the trial at any time, and he does not have to give a reason for withdrawal. If he chooses to have standard therapy, this will be external beam radiotherapy according to the current DAPROCA guidelines.

Patients, who for some reason do not receive the allocated therapy, are to be treated at the doctor's discretion. The analysis of data will be according to the intention-to-treat principle. Unless the patient

does not accept it, he is followed as all other patients in the trial regarding the primary and secondary endpoints.

For patients not receiving the allocated therapy or withdrawing from the trial at a later point of time, the date of exit from the trial is registered as also the reason if possible. The patient is informed about the burden of follow up before randomization to minimize withdrawal from the trial. The patient can withdraw from the trial without telling a reason at any time.

Possible benefits for society

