Appendix B: Dose constraints

Table 1 below shows isotoxic dose constraints to organs at risk. The Equivalent Dose at 2 Gy fractions known from the conventional 39-fraction treatment regime have been converted to equivalent doses for the two hypo-fractionated schemes using an α/β -value of 3.

Requirements for target coverage for the two hypo-fractionated schemes are listed in table 2. Both tables include priorities designating in which order specific constraints should be fulfilled in case of conflicts between target and OAR. CTVs and certain OARs both have priority 1. This should not lead to conflicts since there are no overlaps between the two.

Table 1

OAR	Normo-fractionated DVH constraint	EQD2 of physical dose	Isotoxic dose: 20 fractions ($\alpha/\beta = 3$)	Isotoxic dose: 12 fractions ($\alpha/\beta = 3$)	Priority
Rectum	$V_{75\text{Gy}} < 2\text{cm}^3$	74 Gy	60 Gy	50 Gy	1
	$V_{70\text{Gy}} < 10\%$	67 Gy	55 Gy	46 Gy	3
	$V_{50\text{Gy}} < 60\%$	43 Gy	46 Gy	31 Gy	3
Urethra	$D_{0.1\text{ccm}} < 85\text{Gy}$	88 Gy	71 Gy	59 Gy	1
	$D_{1\text{ccm}} < 80\text{Gy}$	81 Gy	65 Gy	54 Gy	1
Bowel Bag	$D_{\text{max}} < 78\text{Gy}$	78 Gy	63 Gy	53 Gy	1
Bowel Bag - PTV_5mm	$V_{30\text{Gy}} < 450\text{cm}^3$	23 Gy	20 Gy	18 Gy	3
	$V_{45\text{Gy}} < 195\text{cm}^3$	37 Gy	32 Gy	28 Gy	3
Bladder	$D_{\text{mean}} < 62\text{Gy}$	57 Gy	47 Gy	40 Gy	3
	$V_{80\text{Gy}} < 15\%$	81 Gy	65 Gy	54 Gy	3
	$V_{70\text{Gy}} < 35\%$	67 Gy	55 Gy	46 Gy	3
Femoral Heads	$D_{2\%} < 55\text{Gy}$	48 Gy	41 Gy	35 Gy	3
Body (outside PTVs)	$D_{2\%} < 83\text{Gy}$	85 Gy	67 Gy	56 Gy	3

Table 2

Target volume (X denoting specific dose scheme)	DVH constraint		Priority
	20 fractions	12 fractions	
GTVp_FB_post_X	$D_{\text{mean}} = 75 \text{ Gy} (\pm 1\%)$	$D_{\text{mean}} = 60 \text{ Gy} (\pm 1\%)$	2
GTVp_FB_post_X	$V_{71.25\text{Gy}} > 99.5\%$	$V_{57\text{Gy}} > 99.5\%$	2
CTVp_FB_final_X	$V_{71.25\text{Gy}} > 95\%$	$V_{57\text{Gy}} > 95\%$	3
CTVp_FB_final_X	$D_{0.1\text{ccm}} > 80.25\text{Gy}$	$D_{0.1\text{ccm}} > 64.2 \text{ Gy}$	3
CTVp_X	$V_{57\text{Gy}} > 99.5\%$	$V_{47.5\text{Gy}} > 99.5\%$	1
CTVp_SV_X (T3b)	$V_{57\text{Gy}} > 99.5\%$	$V_{47.5\text{Gy}} > 99.5\%$	1
CTVp_SV_X ($\leq T3a$)	$V_{42.75\text{Gy}} > 99.5\%$	$V_{35.15\text{Gy}} > 99.5\%$	1
CTVn_E_X	$V_{42.75\text{Gy}} > 99.5\%$	$V_{35.15\text{Gy}} > 99.5\%$	1
PTVp_X	$V_{57\text{Gy}} > 98\%$	$V_{47.5\text{Gy}} > 98\%$	2
PTV_SV_X (T3b)	$V_{57\text{Gy}} > 98\%$	$V_{47.5\text{Gy}} > 98\%$	2

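### The protocol says urethral dose with boost is kept at the non-boost level, but the shared D0.1ccm limit only caps it, several Gy above the usual top of a non-boost plan

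*Protocol*

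**What the plan says.** Under Potential risks for the patient, the protocol states that the boost is tested without increased dose to surrounding organs. It adds that "we will also ensure that dose to urethra is kept the same dose level as the non-boost arm", and then: "However, we cannot completely exclude a higher risk of urinary toxicity".

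The numerical controls are in Appendix B, introduced by "Table 1 below shows isotoxic dose constraints to organs at risk". The urethra has two rows, given here as EQD2, then 20-fraction limit, then 12-fraction limit:
- D0.1ccm (conventional limit 85 Gy): "88 Gy 71 Gy 59 Gy".
- D1ccm (conventional limit 80 Gy): "81 Gy 65 Gy 54 Gy 1", where the last figure is the priority.

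Both rows have priority 1. Table 1 has one column per fractionation schedule and none for boost status.

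The non-boost prescriptions are "20 fractions, no boost: Prostate and seminal vesicles: 60 Gy/ 20 fractions" and "12 fractions, no boost: Prostate and seminal vesicles: 50 Gy/ 12 fractions". Under Radiotherapy planning, target coverage is described as "usually between 95% and 107% of the prescribed target doses".

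**The concern.** A common cap makes the dose in two arms equal only if it sits at about the level that the lower-dose arm reaches anyway. If it sits well above that level, a centre can meet every constraint and still give boost patients a hotter urethra than non-boost patients. The protocol's statement is about the dose kept, not about the constraint applied.

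Two things are at stake. Urinary toxicity is a risk that the protocol itself names for the boost, and equal urethral dose is the mitigation it offers. And if genitourinary events were more frequent with boost, a reader of the protocol would take the excess to have arisen at equal urethral dose, although the plans were allowed to differ.

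**Working it through.** **Inputs.** Prescriptions without boost: 60 Gy/20 and 50 Gy/12. Boost prescriptions: 75 Gy/20 and 60 Gy/12. Usual upper end: 107%. Urethra limits: Table 1. α/β = 3, as Appendix B states for Table 1.

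**Formulas.** EQD2 = D(D/n + 3)/5. Inverse: D = (n/2)[−3 + √(9 + 20·EQD2/n)].

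**Step 1: reproduce Table 1.**
- 85 Gy in 39 fractions: 85(85/39 + 3)/5 = 88.05. The table says 88, which agrees.
- 80 Gy in 39 fractions: 80(80/39 + 3)/5 = 80.82. The table says 81, which agrees.
- D1ccm converted to 20 and 12 fractions: 64.8 and 53.9 Gy. The table says 65 and 54, which agrees.
- D0.1ccm in 20 fractions: 10[−3 + √(9 + 88.05)] = 68.5 Gy. The table says 71.
- D0.1ccm in 12 fractions: 6[−3 + √(9 + 20·88.05/12)] = 56.9 Gy. The table says 59.

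The D0.1ccm entries therefore do not follow from the table's own EQD2. Converting 88 Gy a second time, as if it were physical dose in 39 fractions, gives 70.8 and 58.7 Gy. That would match 71 and 59, but the documents do not show how the entries arose.

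**Step 2: usual top of a non-boost plan.** 1.07 × 60 = 64.2 Gy (EQD2 79.7). 1.07 × 50 = 53.5 Gy (EQD2 79.8).

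**Step 3: distance of each limit from that level.**

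| Limit | Schedule | Limit (Gy) | % of prescription | Above 107% (Gy) | EQD2 of limit | Above 107% (EQD2) |
|---|---|---|---|---|---|---|
| D0.1ccm as stated | 20 fx | 71 | 118.3 | 6.8 | 93.0 | 13.3 |
| D0.1ccm as stated | 12 fx | 59 | 118.0 | 5.5 | 93.4 | 13.6 |
| D0.1ccm recomputed | 20 fx | 68.5 | 114.2 | 4.3 | 88 | about 8 |
| D0.1ccm recomputed | 12 fx | 56.9 | 113.8 | 3.4 | 88 | about 8 |
| D1ccm as stated | 20 fx | 65 | 108.3 | 0.8 | 81.2 | 1.5 |
| D1ccm as stated | 12 fx | 54 | 108.0 | 0.5 | 81.0 | 1.2 |

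**Step 4: a comparison that does not use the 107% figure.** The stated D0.1ccm limits are 71/75 = 94.7% and 59/60 = 98.3% of the boost prescription. Table 2 counts boost coverage at 71.25 Gy and 57 Gy. The 20-fraction limit is 0.25 Gy below that threshold and the 12-fraction limit is 2 Gy above it.

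**Step 5: what would make the statement true.** The stated cap would hold the hottest 0.1 ccm at the non-boost level only if non-boost plans ordinarily reached about 118% of prescription there (about 114% with the recomputed values). The protocol gives no figure for the urethral hot spot in non-boost plans, so taking 107% as its usual top is an assumption.

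**The case against.** The best case for the plan has five parts.

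1. **Same constraint level.** The Organs at risk section describes an isotoxic approach that maintains existing equivalent constraints, and Table 1 applies identical limits with and without boost. On that reading, same dose level means same constraint. This is a possible intention, but it does not rescue the text: a shared cap well above what a non-boost plan usually reaches does not keep the dose the same.

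2. **Priority.** The urethra limits have priority 1 and every focal-boost objective has priority 2 or 3. Boost coverage therefore yields to the urethra, and the QA group reviews the first boost plan per schedule at each centre. This stands. A reader might infer that there is no safeguard, and that would be wrong. But priority enforces the stated number; it does not lower that number to the non-boost level.

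3. **The 107% figure is not a ceiling.** It is described as usual, and Table 2 sets no upper limit for the prostate CTV or PTV. Table 1 allows the body outside the PTVs a D2% of 67 or 56 Gy in every arm, which is about 112% of the prostate prescription (67/60 and 56/50). This stands, so the gap is indicative. It also means one cannot say that the urethra limits act only in boost plans. Still, 112% is below 118%.

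4. **The next sentence is a caveat.** It says a higher urinary risk cannot be excluded, and the section opens by naming late lower urinary tract effects. So the protocol does not hide the toxicity risk. But the caveat concerns toxicity; the statement about dose is left unqualified.

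5. **Urethral dose will be analysed.** Toxicity is to be related to urethral DVHs, and a dose-response analysis is planned after 600 patients. That helps, but the dose-response analysis is blinded to arm, and the protocol describes no comparison of achieved urethral dose by boost status.

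**Conclusion.** The risk section states a property that the constraints do not deliver. The point rests on the D0.1ccm row alone. As stated, that limit is 6.8 Gy (20 fractions) and 5.5 Gy (12 fractions) above the usual top of a non-boost plan, or 13 to 14 Gy EQD2. About 5 Gy of that EQD2 gap comes from entries that do not reproduce from the table's own 88 Gy. With the recomputed values, 4.3 and 3.4 Gy remain, about 8 Gy EQD2. The mismatch is therefore not only a conversion error.

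Two stronger readings are not supported:
- **That both urethra limits allow a clearly higher dose.** D1ccm exceeds the 107% level by only 0.8 and 0.5 Gy, about 1%, and so holds the hottest 1 ccm close to the top of the usual non-boost range.
- **That the excess is 18%, or 21 to 22 Gy EQD2.** That sets a near-maximum cap against a nominal prescription. A non-boost plan also has its hottest 0.1 ccm somewhere in its dose range.

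The figures assume the linear-quadratic model at α/β 3 and 107% as the usual non-boost top. They describe what compliant plans may do, not what centres will do; achieved doses may be lower. The point bears on the stated patient risk and on how a genitourinary difference between boost and no boost is read. It does not touch the sample size or the FFDM analysis.

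**What to change.** - Reconcile the sentence under Potential risks for the patient with the urethra D0.1ccm row of Table 1, so that the risk section describes what the constraints deliver. Whether the text or the limit changes is the sponsor's clinical decision.
- At the same time, check the 71 and 59 Gy entries against the 88 Gy EQD2 in the same row.
- Because equal dose is not guaranteed, tabulate achieved urethral D0.1ccm and D1ccm for boost against no boost, by fractionation schedule, and report this beside the genitourinary toxicity results. The IDMC is a natural recipient during the trial. Dose plan parameters are already collected and urethral DVHs are already to be analysed.

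The cost is a wording amendment and one extra table. If the text is what changes, the risk statement becomes slightly less favourable to the boost.
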